- a. Participants in the intervention group will then be provided via email/text with a link to access the resource (PCT Pocket Guide). They will be asked to review the resource within two weeks.
- b. Participants in the active control group will be provided via email/text with a link to access the control materials [articles and videos compiled from a NIH-supported website (Children and Clinical Studies) into one online resource]. They will be asked to review the resource within two weeks.

Project staff members will monitor resource usage by groups through the LMS. Parents who complete the resources within 2 weeks will receive a \$25 gift card. Approximately two weeks after completing the pretest questionnaire, participants will receive an email and text with a link to access to their online posttest questionnaire. This questionnaire will include the same questions and instructions at pretest as well as consumer satisfaction questions. If the parent completes the questionnaire, they will receive a \$30 gift card. Participants will receive automatic email/text reminders from the study management system if they have not completed the questionnaires or not accessed their assigned online resource.

Measures.

Implementation

The Learning Management System (LMS) will record the amount of time that participants spend with the parent resource (PCT Pocket Guide; active control) and the specific components that were reviewed.

Consumer Satisfaction

Data will be collected on participant feedback about the resource they review through a posttest consumer satisfaction questionnaire (CSQ). The CSQ will consist of the Acceptability of Intervention Measure (AIM), Intervention Appropriateness Measure (IAM), and Feasibility of Intervention Measure (FIM), which are 4 items each using a 5-pt. Likert scale (1=Completely disagree to 5=Completely agree) and have good discriminant validity and reliability (Weiner et al., 2017). Higher scores indicate greater acceptability, appropriateness, and feasibility. Participants will also be asked to rate their satisfaction with the resource's content, format, and usability using a 5-point Likert scale (1 = Strongly disagree to 5 = Strongly agree) with higher

scores indicating greater satisfaction with the resource. Participants will also respond to open-ended questions about what they liked best and least and any suggestions for changes for their assigned resource.

Outcomes

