Preliminary analyses. Psychometric analyses will be conducted to examine the reliability, validity, and distributions of key variables and scales. Handling variables with poor reliability or validity will include modification or elimination of such variables from the analysis data sets. Variables with noticeably skewed distributions will be transformed or categorized to reduce the impact of non-normality on subsequent analyses. Descriptive statistics will also be conducted to examine the distributions, correlations, means, and standard deviations of the outcome variables. Preliminary analysis will include a test of equivalency between the intervention and control groups on demographic characteristics and baseline levels of primary outcome variables using chi-squared analyses for categorical variables and t-tests for continuous variables. Any characteristics that are nonequivalent will be added as covariates in the main analyses. Depending on the level of missingness, missing data will be multiply imputed at the item level. The imputation model will be estimated using the PROC MI procedure in SAS and will include all outcome items and demographic characteristics that will aid in estimating missing data values. Main analyses will be conducted on each of the imputed datasets.

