Main Analyses. Parents’ reports on the acceptability (AIM), appropriateness (IAM), and feasibility (FIM) of both the intervention (PCT Pocket Guide) and active control (NIH-supported website materials) will first be examined through descriptive statistics. Group mean scale scores greater than 3.0 will indicate more than a moderate amount of acceptability, appropriateness, and feasibility for each resource. Next, ANCOVAs will be used to compare AIM, FIM, and IAM scores looking at main effects of condition as well as interactions (parent gender, parent race/ethnicity, child age, research mistrust), including relevant covariates from the preliminary analyses. We will examine the resource completion rates (at least 70% complete) in the entire intervention group, as well as in subpopulations (parent gender, parent race/ethnicity, research mistrust, research familiarity), as another measure of feasibility. Finally, open-ended feedback about what was liked most, least, and suggested revisions will be coded into categories and summarized. The feedback will be used to create a list of necessary edits to increase the relevance of the resource for parents overall, and for subpopulations of parents.

Exploratory Analyses. To examine intervention effects on the outcome variables at posttest, multiple regression analyses will be used with condition (intervention; active control) as the independent variable. Pretest scores for each outcome will be included as predictor variables and outcome variable means will be reported as adjusted posttest scores. Analyses will be intent-to-treat. Demographic characteristics found to be non-equivalent between the two groups will be included as covariates in the regression models. In addition, moderator analyses will examine intervention effects for subpopulations (e.g., race/ethnicity, sex, research mistrust) to provide evidence regarding how the impact of the PCT Pocket Guide may potentially vary as a function of these characteristics.

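### Acceptability ratings exist only at posttest and the stated imputation model omits recorded resource use, so the means judged against 3.0 may be biased upward if low users are both less satisfied and less likely to return

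*Combined protocol and SAP*

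**What the plan says.** **Collection of ratings.** Under Consumer Satisfaction in the protocol's Measures section: "Data will be collected on participant feedback about the resource they review through a posttest consumer satisfaction questionnaire (CSQ"). AIM, IAM and FIM are part of it, "which are 4 items each using a 5-pt. Likert scale (1=Completely disagree to 5=Completely agree"). The Procedure section confirms that these questions are added at posttest: "This questionnaire will include the same questions and instructions at pretest as well as consumer satisfaction questions". They have no pretest value.

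**Who is asked.** "Approximately two weeks after completing the pretest questionnaire, participants will receive an email and text with a link to access to their online posttest questionnaire". No condition on finishing the resource is stated. The posttest has its own incentive ("If the parent completes the questionnaire, they will receive a" $30 gift card), separate from the $25 card for completing the resource, and automatic reminders are sent.

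**Resource use.** Under Implementation: "The Learning Management System (LMS) will record the amount of time that participants spend with the parent resource", in both arms, together with the components reviewed.

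**Missing data.** Under Preliminary analyses, the SAP makes multiple imputation depend on how much is missing and gives no threshold. The model "will include all outcome items and demographic characteristics that will aid in estimating missing data values". Neither LMS use nor a sensitivity analysis for missing ratings is mentioned.

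**Use of the ratings.** Under Main Analyses, the ratings "will first be examined through descriptive statistics". A group mean above 3.0 is read as more than moderate acceptability, appropriateness or feasibility. ANCOVAs then compare the arms. Completion rates in the intervention group are reported as a separate feasibility measure.

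**The concern.** A parent who does not return loses all 12 rating items (3 scales of 4) together. What the stated model can still use for that parent is pretest outcomes and demographics. Both predate the resource, so neither records how the parent reacted to it. Imputed ratings will then sit close to those of parents who did return.

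The LMS log is the only record described in the documents that postdates exposure and does not depend on a posttest return. It is left out of the step where it would help most.

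Feasibility is the trial's stated objective, these ratings come first in the Main Analyses, and the benchmark is a bare cut-off with no margin or confidence bound. A modest upward shift matters when a mean lies near 3.0. If the shift differs by arm, the ANCOVA comparison would favour the resource that lost more dissatisfied parents.

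**Working it through.** The documents give no sample size, SD, expected rating or dropout rate, so there is no planned figure to reproduce. The inputs below are assumptions unless marked otherwise.

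**1. General identity.** Let d be the proportion not returning and g the mean rating of returners minus that of non-returners. Then bias of the returners' mean = d × g.

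| d | g = 0 | g = 0.5 | g = 1.0 |
|---|---|---|---|
| 10% | 0 | 0.05 | 0.10 |
| 20% | 0 | 0.10 | 0.20 |
| 30% | 0 | 0.15 | 0.30 |
| 40% | 0 | 0.20 | 0.40 |

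The full-group mean exceeds 3.0 (the SAP's criterion) only if the returners' mean exceeds 3.0 + d × g; for d = 20% and g = 1.0 that is 3.20.

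**2. Non-return driven by use.** Let use be standard normal and correlate r with rating; rating SD 0.9. Mean use is −1.091 in the lowest third and +0.545 in the rest.

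*Strong pattern:* non-return 45% in the lowest-use third and 7.5% otherwise.
- Overall non-return = 0.45 × 1/3 + 0.075 × 2/3 = 0.20.
- Mean use of returners = (0.55 × 1/3 × −1.091 + 0.925 × 2/3 × 0.545) / 0.80 = 0.170.
- Bias = 0.9 × r × 0.170 = 0.05, 0.08, 0.11 for r = 0.3, 0.5, 0.7.

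*Mild pattern:* 30% and 15%.
- Overall non-return = 0.30 × 1/3 + 0.15 × 2/3 = 0.20.
- Mean use of returners = (0.70 × 1/3 × −1.091 + 0.85 × 2/3 × 0.545) / 0.80 = 0.068.
- Bias = 0.9 × r × 0.068 = 0.02, 0.03, 0.04.

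With r = 0, or equal non-return across use levels, the bias is 0.

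**3. Does the stated imputation help?** I simulated 2,000,000 records per case with a true mean of 3.00, adding a pretest predictor correlated 0.2 with rating. In the strong pattern:

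| Estimate | r = 0.3 | r = 0.5 | r = 0.7 |
|---|---|---|---|
| Returners only | 3.05 | 3.08 | 3.11 |
| Imputed from pretest | 3.05 | 3.08 | 3.11 |
| Imputed from pretest and use | 3.00 | 3.00 | 3.00 |

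The last row is exact only because use is the sole cause of non-return in this set-up.

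**4. When dislike itself also drives non-return.** A second simulation used true mean 3.5, SD 0.8, use-rating correlation 0.5 and pretest-rating correlation 0.2, with non-return depending on both use and rating:

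| Non-return | Bias, imputed from pretest | Bias, use added |
|---|---|---|
| 10% | +0.09 | +0.05 |
| 20% | +0.17 | +0.10 |
| 30% | +0.24 | +0.14 |
| 40% | +0.31 | +0.20 |

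Adding use helps but leaves more than half of the bias.

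**5. Arm comparison.** The bias in the difference is the difference between the two arms' biases. With the strong pattern in one arm and the mild pattern in the other, at r = 0.5, it is 0.08 − 0.03 = 0.05. With the same pattern in both arms it is 0.

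**The case against.** A reader might infer that the means *are* biased upward and that parents who gave up on a resource are simply given the ratings of those who stayed. The documents do not support that.

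- **Quitting the resource is not missing the posttest.** The link goes out regardless of completion, with its own $30 card and reminders. Only parents who also fail to return lack a rating. This stands and would reduce the bias. It also helps the fix, because low users who return supply the data for imputing those who do not.
- **Imputation is conditional and is not a plain copy.** It depends on the level of missingness, and it conditions on outcome items and demographics. True, but without imputation the mean rests on returners alone, and a weak pretest predictor changed nothing to two decimals. A strong pretest predictor would do better; nothing in the documents shows there is one.
- **LMS data are not ignored.** Completion is reported for the intervention group, so disengagement there will be visible beside the ratings. It is not named as a predictor of missing ratings, and no completion rate is planned for the control arm.
- **The size depends on the set-up.** A true mean of exactly 3.00 makes any bias cross the line; at 3.5, a shift of 0.09 changes no verdict. With SD 0.9, the standard error of an arm mean is 0.9/√50 = 0.13 for 50 raters and 0.9/√100 = 0.09 for 100 (assumed sizes), so most of the range is no larger than sampling error. This stands, although bias does not shrink with more parents.
- **The SAP does not say its predictor list is exhaustive.** LMS use could be added without contradicting it. That makes the change easy, but it does not commit the analyst to it.

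**Conclusion.** The concern holds as a risk, not as a demonstrated bias. Ratings are posttest-only, the stated predictors available for a non-returner all predate exposure, and a relevant recorded variable is not named. If low use goes with both lower satisfaction and non-return, the means compared with 3.0 may be too high by about 0.02 to 0.11 points (assumed: 20% non-return, SD 0.9, use-rating correlation 0.3 to 0.7, and the two non-return patterns above). The bias is zero if use is unrelated to rating or to non-return, and larger if dislike itself keeps parents away. The arm comparison is affected only if the pattern differs by arm. A bias of this size could change the reading of a mean close to 3.0 but not of one well above it.

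Nor should a reader infer that adding LMS use cures the problem. It does so only if use explains the non-return.

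**What to change.** In the SAP, Preliminary analyses:

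1. Add LMS total time and the proportion of components reviewed to the PROC MI model as auxiliary predictors, in both arms.
2. Add one delta-adjusted sensitivity analysis: lower the imputed AIM, IAM and FIM ratings of non-returners who opened the resource, for example by 0.5 and 1.0 point, and report whether the 3.0 criterion and the arm comparison still hold. If 20% of parents are such non-returners, these steps lower the mean by 0.20 × 0.5 = 0.10 and 0.20 × 1.0 = 0.20.
3. Report posttest non-return by arm.

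The plan should also say whether a rating is defined for a parent who never opened the resource, since neither step 1 nor step 2 settles that.

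The cost is some SAP wording and a few lines of SAS, with no extra data or burden on parents. The downside is two more variables in the imputation model and possibly slightly less favourable means.

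### The listed imputation model does not name study condition or its planned interactions; if whole missing posttests are imputed from it, condition differences shrink by about the fraction missing

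*Combined protocol and SAP*

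**What the plan says.** The SAP, under Preliminary analyses, makes imputation conditional: "Depending on the level of missingness, missing data will be multiply imputed at the item level". It gives no threshold. It then describes the PROC MI model, which "will include all outcome items and demographic characteristics that will aid in estimating missing data values". Condition does not appear in that list, nor does any condition-by-moderator term, and nothing says that the arms are imputed separately. The paragraph ends: "Main analyses will be conducted on each of the imputed datasets".

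The analyses that follow are built on condition. Under Main Analyses, "ANCOVAs will be used to compare AIM, FIM, and IAM scores looking at main effects of condition as well as interactions", with research mistrust, child age, and the parent's gender and race/ethnicity as the interacting variables. Under Exploratory Analyses, "multiple regression analyses will be used with condition (intervention; active control) as the independent variable", adjusted for pretest, followed by moderator analyses. That paragraph also says: "Analyses will be intent-to-treat".

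The Study Protocol (Methods, Procedure) makes the posttest a separate online questionnaire, sent by its own link about two weeks after the pretest. AIM, IAM and FIM are collected only then.

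**The concern.** An imputation model should contain every variable whose effect the analysis estimates. If condition is left out, missing outcomes are drawn as though condition made no difference given the other variables. How much that matters depends on what else has been observed for the parent.

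A parent who never opens the posttest link has no posttest items at all. What remains from the list is pretest items and demographics. The pretest is completed before either resource is opened, so under randomization these variables carry no systematic information about arm. Such parents in both arms are imputed from the same pooled distribution, and the imputed part of the data contributes no condition effect.

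At stake are the between-group contrasts in a trial with a superiority framework. The bias is present even when data are missing completely at random, and a larger sample does not remove it. The estimates carried forward to a later trial would be too small. If AIM, IAM and FIM are imputed, each arm's mean is also pulled toward the pooled mean before it is compared with the 3.0 benchmark.

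**Working it through.** The plan states no sample size, effect size or dropout rate, so there is no figure of its own to reproduce. The check has three parts: the expected shrinkage, two simulations of it, and an item count.

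**1. Expected shrinkage.** Let D be the true condition difference adjusted for pretest, and f the fraction with the whole posttest missing, equal in both arms. Observed parents contribute D; parents imputed without condition contribute 0.

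Expected estimate = (1 − f) × D + f × 0 = (1 − f) × D.

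At f = 10%, 20% and 30% this is 0.90 D, 0.80 D and 0.70 D.

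**2. Simulation.** All inputs here are assumptions, not figures from the documents.

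*Setting A:* 100 parents per arm, D = 0.50, five pretest and five posttest items on one factor, values missing completely at random, 5 imputations, 600 replicates, Monte Carlo standard error about 0.005 for the estimates without condition.

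| Missing | Whole posttest missing: without condition | with condition | One posttest item missing: without condition | with condition |
|---|---|---|---|---|
| 5% | 0.466 | 0.488 | 0.495 | 0.510 |
| 10% | 0.445 | 0.505 | 0.496 | 0.500 |
| 20% | 0.403 | 0.500 | 0.498 | 0.496 |
| 30% | 0.352 | 0.495 | 0.502 | 0.489 |

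With whole posttests missing and no condition term, the ratios to the true 0.50 are 0.93, 0.89, 0.81 and 0.70, close to 1 − f. Adding condition restores 0.49 to 0.51. When only one of the five items is missing, the parent's other posttest items carry the effect and there is no visible shrinkage.

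*Setting B:* 100 per arm, D = 0.40 SD, pre-post correlation 0.6, whole posttests missing, 20 imputations, 600 simulated trials.

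| Missing | Without condition | Loss | With condition |
|---|---|---|---|
| 10% | 0.365 | 1 − 0.365/0.40 = 9% | 0.396 |
| 20% | 0.316 | 1 − 0.316/0.40 = 21% | 0.408 |
| 30% | 0.282 | 1 − 0.282/0.40 = 30% | 0.402 |

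Both settings agree with (1 − f) × D. The interaction terms were not simulated. The argument in part 1 applies to them in the same way, because values imputed without a condition-by-moderator term contribute none of that interaction.

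**3. Size of the item-level model.** Counts are from the Study Protocol (Methods, Measures). Closed items per wave:

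- likelihood 2
- willingness up to 5 protocols × 5 questions = 25
- familiarity 1
- attitudes and beliefs 6 + 5 = 11
- decision self-efficacy 11
- research trust 10

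Sum: 2 + 25 + 1 + 11 + 11 + 10 = 60. Two waves plus the 3 × 4 = 12 AIM, IAM and FIM items: 2 × 60 + 12 = 132. With one protocol shown: 2 × 40 + 12 = 92. Knowledge, satisfaction and demographic variables come on top, and the numbers of knowledge and satisfaction items are not given. An unrestricted joint normal model for 132 variables has 132 × 135 / 2 = 8,910 means, variances and covariances. There is no stated sample size to set this against.

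**The case against.** Several stronger readings are tempting, and the documents do not support them.

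- *That the plan excludes condition.* It lists what the model will include and does not say that nothing else enters. Imputing by arm would not list condition as a model variable and would fit the text. This stands as a limit on wording: condition is not named. It does not remove the point, because a programmer following the list would leave condition out.
- *That every imputed value loses the intervention effect and every difference shrinks.* This is so only for wholly missing posttests; scattered item nonresponse gives little bias. Imputation is also conditional on the level of missingness, and no dropout rate is stated.
- *That the AIM, IAM and FIM comparisons are certainly affected.* The protocol places these scales under Consumer Satisfaction, ahead of a separate Outcomes heading, so it is unclear whether the outcome items to be imputed include them. If they are not imputed, this mechanism does not touch them.
- *That the exploratory regressions are certainly affected.* The SAP ties the imputed datasets to the main analyses. The intent-to-treat statement sits under Exploratory Analyses and suggests that non-responders are kept, but does not say how.
- *That the item-level model is too large to fit.* This cannot be shown. The sample size, the number of knowledge items and the PROC MI method are not given, the willingness count is a maximum, and the SAP allows poorly performing variables to be dropped.

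It can also be said that this is a feasibility trial with efficacy labelled exploratory, that the bias is toward no difference, and that the LMS-based completion rate is unaffected. All of that is true and limits the consequences. It does not justify a stated rule that gives a biased contrast when followed and is easily corrected.

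**Conclusion.** The point holds in conditional form. The SAP states what goes into the imputation model, and that list leaves out the factor on which every between-group analysis rests, together with its planned interactions. If the model is built as listed and parents with no posttest are imputed, the condition difference is attenuated by about the missing fraction: roughly 10%, 20% and 30% at 10%, 20% and 30% dropout. Those dropout rates are assumptions, and the result supposes similar dropout in both arms and data missing completely at random. With only scattered items missing, the bias is negligible.

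Whether the AIM, IAM and FIM contrasts and the exploratory regressions are reached depends on whether they use imputed data, which the text leaves open. The size of the item-level model is a secondary caution, not a demonstrated error.

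**What to change.** In the SAP, under Preliminary analyses, state one of two things: that imputation is done separately by arm, or that the imputation model also contains condition and the condition-by-moderator terms tested under Main Analyses and Exploratory Analyses. Imputing by arm covers all the condition interactions at once but leaves only one arm's records for each model; adding terms keeps the arms together but requires each interaction to be listed. Adding condition alone would protect the main effect but not the moderator tests.

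In the same edit, say whether AIM, IAM and FIM are imputed and whether the exploratory regressions use the imputed datasets. Once a sample size is stated, name the PROC MI method and say how the item-level model will be kept estimable.

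Using the LMS usage records as auxiliary variables, imputing scale scores when a whole wave is missing, and fixing the number of imputations are reasonable refinements, but the correction does not depend on them.

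The cost is a sentence or two of SAP text and a few lines of SAS, with no new data. It is best done before outcome data are examined, so that the change cannot look data-driven.

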The study type is interventional and the study model is parallel assignment with a 1:1 allocation ratio and superiority framework to examine the feasibility of the PCT Pocket Guide. The randomized controlled trial will be conducted online at two time points: 1) baseline/pretest and 2) posttest (two weeks after pretest). The study questionnaires will be programmed into an online data collection system. The resources (intervention and active control) will also be completed online by participants. Participants will be randomized, stratifying based upon race/ethnicity (white and not Hispanic/Latino; nonwhite and/or Hispanic/Latino) to one of two conditions: 1) intervention (access to PCT Pocket Guide) or 2) active control (access to control materials compiled from a NIH-supported website). Participants are randomized and enrolled based on: 1) time study forms (i.e., consent) were completed, 2) confirmation of email addresses, 3) their reported demographics collected in the eligibility screener questions, 4) address verification, and 5) indication that they learned about the study from one of the targeted school districts. One of the Co-Principal Investigators will generate the allocation sequences using a random number generator in Excel, assign participants to condition (either intervention or active control) according to those sequences, and enroll participants in the study. The allocation sequence will be stored in a folder on a secure, password-protected server. All participants will be assigned a unique ID number that will be associated with their data (questionnaires; resource use) in place of their name. All personally identifiable information (PII) will be saved on iRT's password protected server, and kept separate from data.

Methods:

Sample and Recruitment.

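### The AIM, IAM and FIM benchmark labels any observed mean above the scale midpoint as more than moderate, with no allowance for sampling error

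*Combined protocol and SAP*

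**What the plan says.** Feasibility is the stated purpose of the trial. The Design section describes "parallel assignment with a 1:1 allocation ratio and superiority framework to examine the feasibility of the PCT Pocket Guide", and the SAP places feasibility under Main Analyses and efficacy under Exploratory Analyses.

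The three lead measures are defined in the protocol (Measures, Consumer Satisfaction) as "4 items each using a 5-pt. Likert scale (1=Completely disagree to 5=Completely agree", and "Higher scores indicate greater acceptability, appropriateness, and feasibility". No label is given for the middle response.

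In the SAP (Main Analyses) the scores "will first be examined through descriptive statistics", and the benchmark follows: "Group mean scale scores greater than 3.0 will indicate more than a moderate amount of acceptability, appropriateness, and feasibility for each resource". The inferential step after it is between arms: "Next, ANCOVAs will be used to compare AIM, FIM, and IAM scores looking at main effects of condition as well as interactions".

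Completion is a further feasibility measure: "We will examine the resource completion rates (at least 70% complete) in the entire intervention group", and then in subpopulations. The control arm is not mentioned there. The protocol (Procedure; Measures, Implementation) has the learning management system (LMS) record use of both resources, and offers the same $25 gift card for completing either one.

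**The concern.** Two features of the benchmark combine badly. The cut-off sits at the middle of a disagree-to-agree scale, yet exceeding it is described as more than moderate endorsement. The cut-off is also applied to the observed mean alone, so 3.01 earns the same description as 4.5, whatever the number of respondents or the spread.

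A report would probably carry the label forward as the finding on acceptability, appropriateness and feasibility, and no other numeric criterion is given for these three constructs. The later ANCOVAs do not repair this. They ask whether the arms differ, and two resources could differ while one or both sit at the midpoint, or fail to differ while both do.

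Completion has a related but smaller gap: no interval is planned, and no control-arm rate is planned beside the Guide's rate.

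**Working it through.** **Inputs from the documents.** Four items per scale, each scored 1 to 5; benchmark: observed group mean above 3.0; allocation 1:1. The documents give no sample size, SD, between-scale correlation or confidence level, so there is no stated figure to reproduce. Those inputs are assumed below and shown as ranges.

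**1. Position of the cut-off.** Midpoint = (1 + 5)/2 = 3.0, the same as the benchmark.

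**2. One scale, true mean 3.0.** P(observed mean > 3.0) = 1 − Φ(0) = 0.50, for any sample size and SD. Simulated four-item, five-point scales symmetric about 3 (20,000 runs per setting; 20, 50 and 100 per arm; scale SD about 0.87) gave 48% to 50%. The shortfall comes from ties at exactly 3.0.

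**3. All three scales, true means 3.0.** With a common correlation r between the scale means, P(all three > 3.0) = 1/8 + [3/(4π)]·arcsin(r).
- r = 0: 0.125
- r = 0.7: 0.125 + 0.2387 × 0.7754 = 0.310
- r = 0.9: 0.125 + 0.2387 × 1.1198 = 0.392

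The ceiling is 0.50, as r approaches 1.

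**4. True mean slightly below the midpoint.** P = Φ[(2.90 − 3.0)/(SD/√n)]. At a true mean of 2.90 and SD 0.6 to 1.0, one scale earns the label 23% to 33% of the time with 20 per arm, 12% to 24% with 50, and 5% to 16% with 100.

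**5. With a lower-limit rule.** The 95% limit exceeds 3.0 when the observed mean exceeds 3 + t(0.975, n−1)·SD/√n. With n = 50, t = 2.010 and √50 = 7.071:
- SD 0.7: 3 + 2.010 × 0.7/7.071 = 3.20
- SD 0.9: 3 + 2.010 × 0.9/7.071 = 3.26

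Over a wider assumed range, the observed mean needed is:

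| n per arm | SD 0.6 | SD 0.8 | SD 1.0 |
|---|---|---|---|
| 20 | 3.28 | 3.37 | 3.47 |
| 50 | 3.17 | 3.23 | 3.28 |
| 100 | 3.12 | 3.16 | 3.20 |
| 150 | 3.10 | 3.13 | 3.16 |

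Under this rule a resource with a true mean of 3.0 is called above the midpoint about 2.5% of the time per scale (2.3% to 2.6% in the simulation).

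**6. Precision of a completion rate (illustrative counts).** Wilson 95% intervals: 35/50 = 70%, 56% to 81%; 7/10 = 70%, 40% to 89%.

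**The case against.** **Any cut-off has this property.** When the truth equals the cut-off, an observed mean exceeds it half the time, whether the cut-off is 3.0 or 4.0. That is correct, and the 50% figure alone does not show that 3.0 is a poor choice. What stands is the combination: the cut-off is the midpoint, the estimate carries no margin, and the label claims more than a position just above the middle.

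**Neutral is an inference.** The protocol labels only the two ends of the scale, and a mean of 3.0 could also come from a split between approval and disapproval. Neither reading supports calling it moderate endorsement.

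**The benchmark is descriptive.** Means are only the first step; completion, the ANCOVAs and coded open-ended feedback follow, and no progression decision is tied to 3.0. This stands and limits the harm. A reader might infer a formal gate with a 50% type I error, but the plan contains no such test.

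**The 70% figure may not be a threshold for the group.** It can be read as a target for the share of parents who complete, or as the definition of a completer (someone who finishes at least that share of the resource). The second reading is plausible because the LMS records which components were reviewed. The documents do not settle it, so it cannot be asserted that the plan judges a group rate against 70%.

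**The control rate does not isolate the gift card.** A reader might infer that adding control-arm completion would separate the effect of the payment from the appeal of the Guide. It would not: both arms are offered the same $25, so the comparison is of two resources under equal payment. It is still worth reporting on those terms.

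**Conclusion.** The concern holds as a point about interpretation. A resource with a true mean at the midpoint would be described as more than moderately acceptable, appropriate or feasible about 50% of the time on each scale, a result that needs no assumption about sample size or SD. It would be tempting to say that such a resource is found feasible overall half the time. The documents do not support that, because they do not say whether one, two or all three scales must exceed 3.0. If all three must, the figure is 31% to 39% for an assumed correlation of 0.7 to 0.9, and 12.5% if the scales are uncorrelated.

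The consequence is an unsupported conclusion on the trial's main objective, not a wrong formal decision. The completion point is secondary: an undefined 70%, no interval, and no planned control-arm rate, with data for both arms already being recorded.

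**What to change.** In the SAP, Main Analyses:

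1. Report each AIM, IAM and FIM group mean with its 95% CI, pooled across imputations if the multiple imputation described under Preliminary analyses is used.
2. Replace the benchmark with: *a scale is called above the midpoint only if the lower 95% confidence limit of the group mean exceeds 3.0*. Delete the wording about a moderate amount. With a large sample a mean barely over 3.0 would still qualify, so the claim should stay at above the midpoint. If the sponsor wants to claim more, a higher level should be named and justified in advance.
3. State whether the feasibility conclusion needs all three scales, and give the planned number per arm so that precision can be judged.
4. Report completion in both arms with Wilson 95% CIs, and the between-arm difference with its CI, as a comparison of the two resources under equal payment.
5. State whether 70% is a group target or a per-parent definition of completion. Read it against the interval only if it is a group target.

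The cost is SAP wording. The posttest and LMS data are already planned, so nothing new is collected. The downside is a slightly harder benchmark: an observed mean of about 3.20 to 3.26, instead of anything over 3.0, under the assumed 50 per arm and SD 0.7 to 0.9.
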